If appropriate describe secondary or post hoc analyses of primary outcome(s) or other exploratory analysis and if necessary, provide a breakdown of the methods used per outcome or endpoint:

Statistical Method to Inform Randomization Bias: Intent to treat bias. To establish equivalence of randomly assigned groups pre-intervention, t-tests will be performed on outcome measures comparing the groups. Means and standard deviations will be obtained and effect sizes calculated. Demographic profiles will be obtained and bivariate significant tests performed to assess the balance expected with randomization. Cohort effects on outcome as well as participation rates will be evaluated to assess any bias related to location, calendar time, or other session characteristics. Participation rates across the intervention will be tracked and compared between the randomized groups. In the spirit of the intent to treat principle (White, Carpenter, and Horton 2012) every effort will be made to conduct follow-up assessments on all randomized participants. Withdrawals will be documented with reason provided. In addition, multi-level modeling allows all cases to remain in a repeated measures model and will be done as a sensitivity analyses to primary analyses done on individuals with at least one follow-up point.

Sample Size Determination: Explain how the overall target sample size was determined (e.g., power analysis; precision estimation), providing justification of the effect size for the primary outcome based on preliminary data, current knowledge/literature and/or cost consideration; if appropriate, provide sample size justification for secondary outcomes. Power analysis should (at least) match the primary outcome/endpoint:

Sample Size. This exploratory study will employ a parallel-group randomized clinical trial design in which 48 participants will be randomly allocated to one of two (2) treatment/intervention groups (AAI and Control) delivered across four (4) cohorts in two (2) waves over the span of two (2) years ($n = 12$ per parallel ten-week cohort) in efforts to inform the specific aims of the study.

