Power & Expected Effect Size. Sample size analysis was conducted for randomized controlled design, using SAS PROC power. For the primary analysis of the main outcome domain (Aim 1: ADHD Behavior) with type I error rate of .05 was implemented for a repeated measures analysis evaluating group main effect, treatment main effect, as well as the group*treatment interaction. Effect size estimates from the authors' previous parallel-group randomized study of HAI demonstrated large AAI vs control effect size for problem behaviors (.86) and moderate effects on inattention (.45) ([name] et al., 2018a). For Aim 1, with a projected analysis of $n=48$, this exploratory study will exceed 90% power to detect effect sizes of .19 and above. At a level of 80% power, the minimum detectable effect was determined to be .21. For Aim 2, $n = 48$ will, for each of the two primary physiological outcome domains (Aim 2: Diurnal Pattern Hypothalamic Pituitary Adrenal axis activity; HPA and Autonomic Nervous System activity; ANS), a multilevel model will be constructed to assess pre-post intervention change, post-follow up change, group differences at each assessment, and group differences in degree of change. Models will account for within-subject correlation and within-cohort correlation. Four (4) cohorts of 13 participants each will be recruited for a total enrolled target sample size of 52 families over Years 1 and 2, accounting for an anticipated attrition rate of about 8% which is based on our recently completed study of AAI with ADHD ([name], et al., 2018a) in efforts to yield a total sample of 48.

Research Procedures

Provide a detailed chronological description of the clinical or treatment plan:

See Study Design

List all procedures involving the use and/or collection of photographs, or audio/video recording:
Facial image will be in video or photo Participants' first names may be collected or recorded in either video or audio recording

Specify the total duration of a subject's participation in the study and clearly outline the duration of participation for each study visit and sub-study, as applicable:

See Study Design

List data collection tools (e.g., measures, questionnaires, observational tool) below by clicking the 'Add Line' button. Include additional rows for study instruments, as needed:

The 'Columns' button allows you to display or hide columns in the Study Instrument List.

Name of Tool:

The Child's Sleep Habits Questionnaire (Owens, Spirito, & McGuinn 2000)

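### Baseline t-tests cannot establish that the arms are equivalent: with about 24 per arm they pass imbalances larger than the prior inattention effect (.45)

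*Combined protocol and SAP*

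**What the plan says.** The relevant text is in the combined protocol and SAP, Statistical Considerations, in the answer on secondary and post hoc analyses headed Statistical Method to Inform Randomization Bias. On the outcome measures it says: "To establish equivalence of randomly assigned groups pre-intervention, t-tests will be performed on outcome measures comparing the groups". The next sentence adds: "Means and standard deviations will be obtained and effect sizes calculated". On the other baseline variables it says: "Demographic profiles will be obtained and bivariate significant tests performed to assess the balance expected with randomization".

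The section gives no equivalence margin, no significance level for these tests, and no action that follows from either result. Neither the description of methods by aim nor the Power & Expected Effect Size paragraph names a baseline covariate for any Aim 1 or Aim 2 model. The same power paragraph lists, among the Aim 2 contrasts, "group differences at each assessment". The pre-intervention visit is one of the three assessments.

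**The concern.** The stated purpose and the stated method do not match. A t-test takes no difference as its null hypothesis. Failing to reject that hypothesis in a small sample is weak evidence of anything, and it is not evidence that the arms are equivalent. Nor does the test address randomisation bias. If allocation was properly random, every baseline difference is chance, so the p-value tests a hypothesis already known to be true. The same applies to the demographic tests meant "bivariate significant tests performed to assess the balance expected with randomization".

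Two things are at stake. First, a report that the arms were shown to be equivalent would be unsupported, and readers may rely on it when they take an unadjusted arm difference as the effect of the dogs. Second, no baseline adjustment is pre-specified. The baseline check is therefore the only step in the plan directed at chance imbalance, and at this sample size it is a poor guard.

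**Working it through.** **Inputs from the documents**
- Analysed sample: "48 participants will be randomly allocated to one of two (2) treatment/intervention groups (AAI and Control" arms). Equal allocation is not stated; 24 per arm is assumed.
- Enrolment: four cohorts of 13, "for a total enrolled target sample size of 52 families over Years 1 and 2, accounting for an anticipated attrition rate of about 8" per cent. At most 26 per arm would then be present at baseline.
- Level: the Aim 1 sample-size analysis was run "with type I error rate of .05 was implemented for a repeated measures analysis evaluating group main effect". Sidedness is not given, and no level is given for the baseline tests; two-sided .05 is assumed.
- Prior effects (power paragraph): .86 for problem behaviors and .45 for inattention. The metric is not stated; they are read as Cohen's d.

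The plan gives no figure for the baseline tests, so there is none to reproduce. Its Aim 1 power figures are not used here.

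**1. Largest observed imbalance that is non-significant**

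Standardised difference = t(1 - alpha/2, 2n - 2) x sqrt(2/n). For n = 24 at .05: 2.013 x 0.2887 = 0.581 SD.

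| Per arm | Two-sided level | Threshold (SD) |
|---|---|---|
| 22 | .05 | 0.608 |
| 24 | .05 | 0.581 |
| 26 | .05 | 0.557 |
| 24 | .10 | 0.485 |
| 24 | .20 | 0.375 |

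The first four rows exceed .45, and every row is below .86. Only a level as loose as .20 brings the threshold under .45.

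**2. Chance of missing a true difference**

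Noncentrality = d / sqrt(2/24), with 46 df.
- d = 0.45: 0.45 / 0.2887 = 1.559; non-significant with probability 0.667.
- d = 0.86: 0.86 / 0.2887 = 2.979; non-significant with probability 0.169.

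**3. How often a sizeable imbalance passes under correct randomisation**

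P(|observed d| > 0.45) = 2 x P(t46 > 1.559) = 0.126. Removing the 0.05 that would be significant leaves 0.076, or about 7.6% per outcome.

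**4. Effect of a 0.58 SD imbalance on later comparisons**

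Assume equal SDs at each visit, no treatment effect, and a correlation r of .5 to .7 between baseline and later visits. The documents do not give r. A positive sign means the direction of the imbalance.
- Unadjusted post comparison: 0.581 x r = 0.29 to 0.41 SD.
- Change from baseline: 0.581 x (r - 1) = -0.29 to -0.17 SD.
- Group main effect averaged over three visits, if baseline is one of them: 0.581 x (1 + 2r)/3 = 0.39 to 0.46 SD.

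**5. Would a formal equivalence test rescue the claim?**

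The 90% confidence interval for the baseline difference has a half-width of 1.679 x 0.2887 = 0.485 SD, already wider than a 0.45 margin. Two one-sided tests at .05, with that margin in population SD units and a true difference of zero, succeed about 2% of the time. About 85 per arm would be needed for 80% power.

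**The case against.** The strongest reply is that this is a wording fault in a descriptive check. Several parts of that reply stand.

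- **Effect sizes are already planned.** A 0.5 SD imbalance would appear in the baseline summary whatever its p-value. This is true, but no threshold or action is attached to the effect sizes, and the claim of equivalence is tied to the t-tests.
- **Nothing depends on the result.** A reader might infer a rule under which non-significance certifies the arms and significance triggers a choice of covariates. The documents contain no such rule. Reading non-significance as equivalence follows from the stated purpose; data-driven adjustment is only a possibility.
- **The main analyses use repeated measures or change.** These deal with part of an imbalance, but not all of it. Change contrasts shift in the opposite direction through regression to the mean, by no more than 0.29 SD under the assumptions above. The 0.29 to 0.41 SD figure belongs only to an unadjusted post comparison. The Aim 1 group main effect remains exposed if baseline is among the visits averaged.
- **Not every prior effect is smaller than the threshold.** A reader might infer that the test passes imbalances larger than whatever is being replicated. That holds for inattention only: an observed imbalance of .86 would be flagged.

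It is also tempting to quote a chance of at least one false flag across all baseline measures. The documents give no count of those measures, and ratings of one child are unlikely to be independent, so no such figure is offered.

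**Conclusion.** The concern holds in limited form. Using t-tests to establish equivalence is wrong as written, and the demographic tests cannot show whether randomisation was biased. The fault should be corrected because it affects what the trial may conclude about its arms. The main numerical comparison, 0.58 SD against .45, rests on 24 per arm, two-sided .05 and Cohen's d. It survives 22 to 26 per arm, and a level of .10 at 24 per arm. The carry-over figures rest on the assumed correlation.

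A reader might infer that the randomised comparison itself is invalid. The documents do not support that: allocation is random, no primary test depends on the baseline checks, and an imbalance above 0.45 SD that passes unflagged is uncommon for any one outcome. The pre-intervention contrast in the Aim 2 list is a minor matter, since nothing says it will be used to claim equivalence.

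**What to change.** 1. Delete the statement that the t-tests establish equivalence, together with the baseline significance tests on outcomes and demographics.
2. Keep the means, SDs and effect sizes already planned, and present them by arm as a descriptive balance table.
3. Pre-specify adjustment for the baseline value of each outcome in the Aim 1 and Aim 2 group comparisons, whatever the balance table shows.
4. State that any Aim 2 group contrast at the pre-intervention visit is descriptive only.

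Substituting a formal equivalence test is not workable at this size, as step 5 of the working shows. The cost is a few lines of plan wording, one covariate per model, and loss of the equivalence statement. The progress report says that no data had been analysed at that point, so on that record the change could be made before results are seen.

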Statistical Method per Outcome Specific Aim 1: Replicate Previous Favorable Behavioral Response to AAI Primary Main Outcome: Behavior responses. This parallel-group randomized design and will utilize a multi-method and multi-source assessment protocol. The assessment protocol will use a repeated-measure within-subject design, gathering main outcomes at three time points to assess the efficacy of AAI on outcomes for children with ADHD who are participating in a short-term intervention with or without the assistance of certified therapy dogs (see Figure 1). Our previous research indicated that after just 2 weeks of intervention, participants in the AAI condition showed significantly greater improvement in symptoms compared to control participants and that these gains were maximized by 10 weeks and then maintained at 6 weeks post intervention ([name] et al., 2018a), suggesting that 10 weeks is an ideal duration of treatment to detect significant benefits from AAI with dogs. Outcomes from AAI utilizing a manualized treatment with therapy dogs (AAI) will be compared to standard of care evidence-based psychosocial treatment at usual (control). Specific Aim 2: Determine Physiological Response over time to AAI for children with ADHD. Exploratory Main Outcome: Diurnal HPA and ANS responses. To determine if children with ADHD present with measurable changes in physiological responses to a short-term AAI (10 weeks) on measures of HPA and ANS we will gather candidate salivary analytes (salivary cortisol, uric acid, and alpha-amylase; Cort, sUA, sAA, respectively) and measures of cardiac rhythm, (heart rate variability; HRV) prior to and post intervention for children participating in both treatment conditions before, immediately after, and upon treatment follow up. Specifically, for each domain we will ascertain changes in diurnal patterns of candidate physiological measures utilizing a linear, repeated measures design gathered across three (3) points in time; establishing individual baseline patterns, end of treatment patterns, and then patterns at 6 weeks post-treatment. Specific Aim 3; Explore Individual Differences as potential mediators of response to AAI in children with ADHD. Secondary Outcome Exploratory Mediator Analysis; In the proposed study, we will explore how children's individual (a) acute physiological responses during intervention sessions and their individual (b) social interaction quality during intervention sessions may play a role in each of the Main Outcomes. Specifically, we will a) ascertain acute HPA activity (as measured by Cort, and sUA) and acute ANS activity (as measured by HRV and sAA) during intervention sessions across

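### For Aim 1, the multilevel model that keeps all randomised children should be primary and the at-least-one-follow-up analysis the sensitivity analysis; the plan has these roles reversed

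*Combined protocol and SAP*

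**What the plan says.** The relevant text is in Statistical Considerations, in the answer on secondary or post hoc analyses, under the label on intent-to-treat bias. It opens "In the spirit of the intent to treat principle" and promises that "every effort will be made to conduct follow-up assessments on all randomized participants". It then notes that "multi-level modeling allows all cases to remain in a repeated measures model", and gives that model its role: it "will be done as a sensitivity analyses to primary analyses done on individuals with at least one follow-up point". The same answer says that withdrawals will be documented with reasons and that participation will be compared between arms.

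The Aim 1 description has the study "gathering main outcomes at three time points", which the Study Design section places just before treatment, just after it, and some weeks later. The field for the primary analysis method only refers back to the preceding answer. Neither place defines another analysis set, a missing-data assumption or an imputation method.

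The Power & Expected Effect Size section describes Aim 1 as a repeated measures analysis with main effects and an interaction. For Aim 2 it makes a multilevel model, allowing for within-child and within-cohort correlation, the main model. It sets a "total enrolled target sample size of 52 families over Years 1 and 2", "accounting for an anticipated attrition rate of about 8" percent, to end with 48.

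**The concern.** Returning for a follow-up visit happens after randomisation. An analysis set defined by it no longer compares the groups exactly as randomised. The plan names the method that avoids this and gives it the secondary role for the primary aim, while using the same kind of model as the main analysis for an exploratory aim.

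Children without follow-up still matter in a group-by-time analysis, because those lost after the first assessment day have baseline values. Suppose the more severe children leave, and do so more in one arm. Dropping their baselines changes the mean baseline of those who remain, and with it the expected regression toward the mean in that arm. If the losses are in the control arm, the remaining control children appear to improve less and the comparison tilts toward the dog-assisted arm. If the losses are in the dog-assisted arm, it tilts the other way. Families know which arm they are in, so unequal loss is possible.

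**Working it through.** **1. How many children are affected.** From the Power section: 48 to be analysed, about 8% attrition, 52 enrolled.
- 48 / 0.92 = 52.17 and 52 × 0.92 = 47.84, so the plan's step from 52 to 48 reproduces to within rounding.
- Expected losses: 52 − 48 = 4, and 4/52 = 7.7%.
- This is an upper figure for the exclusion. A child lost after the first follow-up stays in the primary set.
- The Sample Size paragraph instead says "48 participants will be randomly allocated to one of two (2) treatment/intervention groups". On that reading, 48 × 0.92 = 44.16, so about 4 are again excluded.

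**2. Size of the bias in an unadjusted change comparison.** Assumptions, none of them stated in the documents: 26 children per arm; outcome standardised to SD 1 at both visits; baseline-post correlation r of .5 or .7; loss depends on baseline only.

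A child with baseline b has expected change −(1 − r)b, apart from the treatment effect. If k of n children are lost from an arm and their mean baseline is m SD above the arm mean, the mean baseline of those who remain moves by −k·m/(n − k). The arm's mean change therefore moves by (1 − r)·k·m/(n − k), and the bias in the group difference is the difference between the arms in this quantity.

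| Assumed loss | Calculation | r = .5 | r = .7 |
|---|---|---|---|
| 4 versus 0, the arm's 4 most severe (expected mean of the top 4 of 26 normal values, m = 1.475) | (1 − r) × 4 × 1.475/22 = (1 − r) × .268 | .134 | .080 |
| 3 versus 1, m = 1 in both arms | (1 − r) × (3/23 − 1/25) = (1 − r) × .0904 | .045 | .027 |
| 3 versus 1, m = 0.5 in both arms | (1 − r) × .0452 | .023 | .014 |
| 2 versus 2, same m | terms cancel | 0 | 0 |
| Any split, loss unrelated to severity | m = 0 | 0 | 0 |

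Simulation agrees: .136 and .079 SD for the extreme case, .046 and .028 SD for a 3-versus-1 loss moderately related to severity, and about zero for 2 versus 2.

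**3. What removes the bias.** In the same simulated extreme case, a likelihood estimate that keeps all baselines has bias of about .002 SD. A baseline-adjusted comparison within the restricted set also has bias near zero (.000 and .001).

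**4. Cost in precision.** Standard error of the group difference, restricted change analysis versus all-cases model: .287 versus .288 at r = .5, and .222 versus .223 at r = .7.

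**The case against.** **No formal breach.** A reader might infer that the plan breaks an intent-to-treat commitment. It does not define an intent-to-treat set. It invokes only the spirit of the principle, mainly in connection with follow-up effort, and it plans the all-cases model, withdrawal reasons and a comparison of participation. This stands: the tension is with a stated aim, not with a defined analysis set.

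**The bias depends on the estimator.** A reader might infer that excluding these children biases the result in itself. When loss depends only on baseline, adjusting for baseline in the restricted set works as well. This also stands. However, the documents specify no baseline adjustment for Aim 1; they describe group-by-time effects and pre-post change, so the unadjusted comparison is a fair reading.

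**The large figure needs an unlikely pattern.** If loss is unrelated to arm, all 4 fall in the same arm about 11% of the time (2 × C(26,4)/C(52,4) = .110), before requiring that they be the most severe. Even the extreme bias is below the sampling error of .22-.29. Expressing it as a share of the .45 inattention effect quoted in the Power section would also be unsafe, because the scale of that figure is not given and .86 is quoted beside it for problem behaviours.

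**Unequal loss is not shown.** A reader might infer that control families will leave more often. Nothing in the documents says so. Both arms receive active group sessions, and the renewal form reports 22 children enrolled with no withdrawals or removals.

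These points limit the severity. None gives a reason to prefer the restricted set as primary when the all-cases model is already planned.

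**Conclusion.** The point holds in a modest form. For Aim 1 the primary set is conditioned on a post-randomisation event, and the model that avoids this has only a sensitivity role. The affected group is at most about 4 of 52 children. The bias in an unadjusted change comparison is about .03-.05 SD under a 3-versus-1, moderately severity-related loss, .08-.14 SD at the extreme, and about zero if loss is balanced or unrelated to severity. All of this rests on an assumed correlation of .5 to .7 and 26 children per arm.

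The documents do not support saying that the Aim 1 result will be biased, only that the planned primary set leaves it open to a bias that the plan can already remove. Two limits remain. The multilevel model corrects this under missing at random, not under loss that depends on unobserved outcomes. A child who leaves before the baseline assessment adds nothing to either analysis; the documents do not state whether randomisation comes before or after that visit. This is a free improvement rather than a serious flaw.

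**What to change.** In the intent-to-treat paragraph, and in the primary-method field that now only refers back:
- Name as the primary Aim 1 analysis a multilevel model on all randomised children in the arm assigned, using every available visit including baseline and accounting for cohort, as the Aim 2 model already does.
- State that it assumes missing at random.
- Report the analysis of children with at least one follow-up as sensitivity.

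The cost is wording only. No new data or analysis is needed, and the standard errors are essentially unchanged. The renewal form states that no data had been analysed at that date, so the change could then have been made without knowledge of results.

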Progress Report

UCI Progress

Please provide a detailed description of the progress of the study, including a brief summary of any interim findings or trends, and plans for the next approval period:

Initial participant recruitment and intervention was delayed by the pandemic, with the first eligibility visits starting in the fall of 2021. Recruitment, screening, eligibility visits, and intervention are presently ongoing. The targeted enrollment for this study is 48-52 participants, with 22 participants consented and found eligible for enrollment to date. A no-cost extension was filed with NIH, extending the research period to 8/31/2023 in an effort to complete recruitment of the targeted sample size indicated by power analysis. No data has been analyzed to date. Full enrollment is targeted for March of 2023, with intervention sessions ending by June, 2023. Data analysis, presentation and publication of findings are expect for Summer 2023.

Relying Entity Progress (as applicable)

If UCI is the IRB of Record for a non-UCI entity, provide a progress report for each relying entity (e.g., number of participants enrolled at the sub-site; data analysis performed, if any, etc):

N/A

Informed Consent

Confirm that there is no new information that raises concerns about the circumstances under which informed consent is being obtained:

No new information

Confirm that any new findings that have developed since the last continuing review, have been provided to enrolled subjects, as appropriate:

No new findings

Confirm that the research team is using the most recently approved version of the consent/assent document and that it contains the most accurate, up-to-date information about the research:

Yes

Confirm that all signed consent documents are on file and available for inspection:

Yes

Specify if any subjects were enrolled using a non-English consent document, information sheet, or script:

No

Given that some research studies have multiple consent/assent forms, please indicate which approved consent/assent forms should be reviewed by the IRB:

Review all consent/assent forms

Re-Consent Status

Are there approved Re-Consent Cover Memos on file?

IMPORTANT! To verify, review the 'Approved' documents in the Attachments section.

Yes

Is the re-consenting of participants complete?

Yes, all reconsenting is complete

REQUIRED! Review and review the Attachments section to remove all re-consent cover memos that are no longer being used.

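### The plan uses 48 both as the number randomised and as the number left after attrition from 52, so the randomised sample size and the recruitment stopping point each have more than one value

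*Combined protocol and SAP*

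**What the plan says.** All places are in the combined protocol and SAP.

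- **Sample Size Determination, Sample Size paragraph.** "48 participants will be randomly allocated to one of two (2) treatment/intervention groups (AAI and Control" arms, in four cohorts with n = 12 "per parallel ten-week cohort".
- **Power & Expected Effect Size, end of the paragraph.** "Four (4) cohorts of 13 participants each will be recruited for a total enrolled target sample size of 52 families", "accounting for an anticipated attrition rate of about 8" per cent, "in efforts to yield a total sample of 48". The 8% is attributed to the team's own completed study of the intervention in ADHD.
- **Power & Expected Effect Size, Aim 1.** "For Aim 1, with a projected analysis of" n = 48.
- **Non-technical summary (Project Screener).** The trial is described as randomised, with 48 children.
- **Enrolment table (Subject Populations).** For children, 48 is the number expected to complete or needed for the research question; the maximum to be consented is 80.
- **Progress Report.** "The targeted enrollment for this study is 48-52 participants", with 22 enrolled so far. A no-cost extension was filed so that the sample size given by the power analysis could be reached.
- **Secondary and post hoc analyses (Statistical Considerations).** The primary analysis uses children with at least one follow-up point. A multilevel model that keeps all cases is a sensitivity analysis.

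**The concern.** The number randomised is one of the few figures in a trial plan that must have a single value. Here 48 is the number entering the randomised comparison in two places and the number remaining after losses in two others, and the cohort size is both 12 and 13. The Progress Report's range covers both values and does not choose between them.

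This matters in practice because recruitment was open when this version was written. A team that closed at 48 randomised would satisfy the Sample Size paragraph, the non-technical summary and the lower end of the Progress Report range. It would not have used the attrition allowance in the power paragraph, and the calculation for 48 analysed would then describe a somewhat larger trial than the one run.

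**Working it through.** **Inputs from the documents:** 48 randomised and 12 per cohort (Sample Size paragraph); 52 enrolled, 13 per cohort, about 8% attrition, 48 remaining, 48 analysed for Aim 1 and type I error .05 (Power & Expected Effect Size); three assessment times (Statistical Methods, Aim 1).

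**1. Reproduce the plan's own figures.**
- Cohorts: 4 x 12 = 48 and 4 x 13 = 52. Each total agrees with its own cohort size.
- Attrition from 52: 52 x (1 - 0.08) = 47.84, about 48.
- In reverse: 48 / 0.92 = 52.17, and (52 - 48) / 52 = 7.7%, which fits a rate of about 8%.

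The allowance in the power paragraph is therefore present and arithmetically sound.

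**2. Apply the same rate to 48 randomised.** 48 x 0.92 = 44.16, about 44. This assumes that all losses come after randomisation and that no lost child contributes a follow-up visit.

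**3. Size of the effect, 48 against 44 analysed.**
- Detectable effect scales roughly as 1/sqrt(N): sqrt(48/44) = 1.044, about 4% larger.
- Two-sample t test, two-sided .05, equal arms (illustration; this is not the plan's repeated-measures test). The standardised difference detectable with 80% power is .826 at 24 per arm and .865 at 22 per arm. Power at the two earlier effect sizes that the plan cites goes from 83.1% to 79.6% at .86, and from 33.3% to 30.8% at .45.
- Group-by-time test in a two-arm repeated-measures ANOVA. The noncentrality is f^2 x N x m / (1 - rho), with m - 1 and (N - 2)(m - 1) degrees of freedom. Assumed: m = 3, sphericity, 1:1 allocation, and the plan's .19 read as Cohen's f. The documents give neither the effect-size metric nor rho, so a range is shown:

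| rho (assumed) | Power at .19, N = 48 | Power at .19, N = 44 |
|---|---|---|
| 0.3 | 66.8% | 62.6% |
| 0.5 | 81.8% | 78.0% |
| 0.7 | 96.5% | 94.8% |

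The loss is about 4 percentage points at most over this range.

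**4. Can the stated power be used as a yardstick?** No. The plan claims more than 90% power at .19 and an 80%-power minimum detectable effect of .21, both for 48. Power rises with effect size, so the two statements contradict each other before any attrition is considered.

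**The case against.** The strongest reply is that attrition has already been handled. The power paragraph is the only text that derives an enrolment target, and it does so correctly; the enrolment table also lists 48 as the number expected to complete or needed. On this reading the Sample Size paragraph and the summary loosely quote the completing number, and the Progress Report is a status statement that sets no stopping rule. This stands as the likelier intent. It does not remove the conflict, because the plan's only sentence on how many are randomised says 48.

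A second reply is that the four losses could fall between enrolment and randomisation, so that 52 enrolled and 48 randomised would agree. The plan does not say where in participant flow the 8% arises, so this cannot be excluded. It is less natural. The maximum of 80 consented already leaves room for screening losses, the Progress Report counts as enrolled those who consented and were found eligible, and initial assessment and randomisation share a 21-day window before treatment. If it were nevertheless the meaning, the plan would hold no allowance for loss after randomisation.

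A third reply is that 44 is too pessimistic. There are two post-baseline assessments, one is enough for the primary analysis, and the renewal form reports no withdrawals among 22 enrolled (8 were still in intervention, so this is partial evidence). That is right, and 44 is a floor under the plan's own rate.

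A reader might go further and infer that attrition costs the trial its stated power. The documents do not support that. The stated power cannot be verified at 48, since the metric and within-subject correlation are missing and its two statements conflict. No verified figure exists to be lost. That contradiction is a separate and larger fault.

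**Conclusion.** The inconsistency is real: 48 or 52 randomised, 12 or 13 per cohort, and a recruitment target of 48-52. The plan most likely means 52 enrolled for about 48 analysed, and on that reading its attrition arithmetic is correct.

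The consequence is conditional and modest. Only if recruitment stopped at 48 randomised would the analysed number fall below 48, to about 44 at worst, with a detectable effect about 4% larger and a power loss of about 3-4 points in most of the illustrated cases. This rests on the plan's 8% applying after randomisation, on no lost child having a follow-up visit, and, for the power figures, on the assumed test, metric and correlations. The main reason to correct it is that it decides when recruitment closes.

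**What to change.** State one number randomised, 52 at 13 per cohort, and one expected number analysed, about 48. Use both consistently in the Sample Size paragraph, the Power & Expected Effect Size paragraph, the non-technical summary and the Progress Report. Say that 52 randomised is the point at which recruitment stops, and that the 8% refers to loss after randomisation. This costs only wording, plus the four further children that the power paragraph already plans for.

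If 48 is truly the number to be randomised, say so, remove the 52, and restate power and detectable effect for the number expected to be analysed (about 44 at worst), naming the effect-size metric and the within-subject correlation. The cost is a slightly less favourable detectable effect.
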